| 5.2. Changes to the SAP..... | 15 |
| 5.2.1. Data Handling Rules..... | 15 |
| 5.3. Primary Efficacy Endpoint..... | 15 |
| 5.3.1. Definition | 15 |
| 5.3.2. Estimand | 16 |
| 5.3.3. Analysis Methods..... | 16 |
| 5.4. Secondary Endpoints | 17 |
| 5.4.1. Definition | 17 |
| 5.4.2. Analysis Methods..... | 17 |
| 5.5. Multiplicity Adjustment..... | 18 |
| 5.6. Exploratory Efficacy Variable(s)..... | 19 |
| 5.6.1. Definition | 19 |

| | |
|--|-----------|
| 5.6.2. Analysis Methods..... | 20 |
| 6. SAFETY | 20 |
| 6.1. Adverse Events | 20 |
| 6.2. Clinical Laboratory Tests..... | 21 |
| 6.3. Vital Signs and Physical Examination Findings | 21 |
| 6.4. Other Safety Parameters | 21 |
| REFERENCES..... | 22 |

AMENDMENT HISTORY

The original SAP (dated 24 May 2019) described analyses of the test-retest variation for each visual function assessment, however, this will not be assessed given that the assessments of efficacy endpoints focus on the effect of the treated eye in immediate treatment group compared to the randomized concurrent control eye in deferred group. The statistics for the test-retest do not fit the purposes of the stated objectives and are not appropriate for the goals of the study. The current SAP describes analyses comparing treated eye in immediate treatment group compared to the randomized concurrent control eye in deferred group. Furthermore, the original SAP did not pre-specify primary/secondary endpoints and hierarchical testing. These are addressed in this SAP.

ABBREVIATIONS

| | |
|--------|--|
| AAV | Adeno-Associated Virus |
| AE | adverse event |
| ATC | Anatomical Therapeutic Chemical |
| ATIMP | advanced therapy investigational medicinal product |
| BMI | body mass index |
| CI | confidence interval |
| RPGR | Retinitis Pigmentosa GTPase Regulator |
| dB-sr | decibel-steradians |
| DLE | dose-limiting event |
| DPS | Data Presentation Specifications |
| EQ-5D | EuroQol 5-Dimension |
| ERG | Electroretinography |
| ETDRS | Early Treatment Diabetic Retinopathy Study |
| eCRF | electronic case report form |
| FAS | Full analysis set |
| FV | Functional Vision |
| IDMC | Independent Data Monitoring Committee |
| IVI | impact of visual impairment |
| IVI-A | impact of visual impairment adult |
| IVI-C | impact of visual impairment child |
| LLQ | Low luminance questionnaire |
| MedDRA | Medical Dictionary for Regulatory Activities |
| meanRS | Mean Retinal Sensitivity |
| PAP | Psychometric Analysis Plan |
| PCR | polymerase chain reaction |
| PRO | Patient-reported Outcomes |
| QoL | Quality of Life |
| RPGR | Retinitis Pigmentosa GTPase Regulator |
| SAE | serious adverse event |
| SAP | Statistical Analysis Plan |
| SD | standard deviation |
| SD-OCT | spectral domain optical coherence tomography |
| SUSAR | suspected unexpected serious adverse reaction |
| V30 | central 30-degree field-of-vision |
| VA | Visual Acuity |
| VFMA | visual field modeling and analysis |
| WHO-DD | World Health Organization Drug Dictionary |
| XLRP | X-linked Retinitis Pigmentosa |

1. INTRODUCTION

This Statistical Analysis Plan (SAP) specifies definitions of analysis sets, key derived variables, and statistical methods for the analysis of safety and efficacy data for the Phase I/II RPGR study (MGT009). This SAP is based on the protocol of study MGT009, v12.0 and replaces the original SAP dated 24 May 2019, with the key change related to the analysis of efficacy parameters as further described in Section 5.1. Titles, mock-ups and programming instructions for all statistical outputs (tables, figures, and listings) are provided in a Data Presentation Specifications (DPS).

1.1. Trial Objectives

The primary research objective is to assess the safety of the advanced therapy investigational medicinal product (ATIMP), AAV5-hRKp.RPGR vector for RPGR-ORF15 gene replacement in the retina of patients with RPGR-XLRP based on the primary safety outcome listed in Section 1.3.1. The secondary research objective is to determine whether an AAV5-hRKp.RPGR vector for RPGR-ORF15 gene replacement in the retina can slow/halt progressive deterioration or possibly even improve retinal structure or visual function, functional vision and vision-related quality of life in patients with RPGR-XLRP. Specifically, the secondary research objective is to evaluate the effect of treatment on the following endpoints: perimetry responder, central 30-degree hill-of-vision, walk time in visual mobility assessment, retinal sensitivity in microperimetry, patient reported outcome, low luminance visual acuity, contrast sensitivity and EZ area.

1.2. Trial Design

This is an open-label, phase I/II dose-escalation trial to determine the safety and efficacy of subretinal administration of the study agent (AAV5-hRKp.RPGR) in subjects with genetically confirmed RPGR-XLRP. As shown in Schema of treatment groups with study phases in Figure 1 and Schema of treatment groups within study phases in Figure 2, MGT-RPGR-009 includes three phases, dose escalation phase in adult RPGR patients, dose confirmation phase in pediatric RPGR patients, and randomized expansion phase in adult RPGR patients.

Figure 1: MGT009 Study Design Schematic

[figure not shown]
[figure not shown]

Figure 2: Schema of treatment groups within study phases

In the dose escalation phase, subjects were administered a single dose of ATIMP in cohorts of 3-4 subjects at a time. Based on a review of safety data, the Independent Data Monitoring Committee (IDMC) made recommendations on whether the dose was to be escalated or whether additional subjects were needed to repeat a dose in the cohort. The IDMC concurred on dosing a pediatric cohort at the intermediate dose prior to moving into the expansion cohort.

After an acceptable safety profile had been established in adults, the IDMC agreed to the sponsor's plan for administering the intermediate and low doses in the expansion phase. In the expansion phase, subjects were randomized to either immediate treatment with the low dose, or immediate treatment with the intermediate dose, or to a 6-month deferred-treatment group to receive either the low dose or the intermediate dose. Subjects in the immediate treatment arm were followed for 12 months before migrating to the long-term extension study, MGT-RPGR-010. Subjects in the deferred treatment arm were followed for at least 6 months before crossing them over to active treatment; at the 12-month time point these subjects also migrated to the long-term follow up study, MGT-RPGR-010. 6-month data from deferred arm during deferred period prior to treatment serves as the concurrent control group.

Adults were defined as subjects aged 16+ in the United Kingdom and aged 18+ in the United States.

Safety and efficacy are assessed for 12 months following the intervention by clinical examination and special investigations according to the schedule in Section 5.6 of the protocol.

The study conduct was substantially impacted by the COVID-19 pandemic. In particular, the pandemic caused delayed and missed visits to several subjects in the randomized dose expansion phase of the study. In addition, there were delays beyond the planned 6 months for treatment in the deferred treatment arm of the study. To allow greater flexibility in the management of protocol

deviations and timing of treatments in the deferred treatment arm of the study as a result of the COVID-19 pandemic, the protocol was amended in accordance with Health Authority guidance.

1.3. Statistical Hypotheses for Trial Objectives

1.3.1. Primary Safety Hypothesis

The objective of the dose escalation phase is to estimate the proportion of subjects who experienced the primary safety outcome. No formal hypothesis testing will be conducted.

The primary safety outcome is defined as any of the events delineated below and occurring during the 9 weeks following administration, at least possibly related to the ATIMP, not the surgery alone:

- Reduction in visual acuity by 15 Early Treatment Diabetic Retinopathy Study (ETDRS) letters or more
- Severe unresponsive inflammation (defined in Section 4.2.1 of the protocol)
- Infective endophthalmitis
- Ocular malignancy
- Grade III or above non-ocular suspected unexpected serious adverse reaction (SUSAR) (Protocol MGT009, Section 5.11.3.4.2 Severity or Grading of Adverse Events).

Safety will be assessed for 12 months following ATIMP administration for immediate treatment participants in this study (Protocol MGT009) by study phases (dose escalation, dose confirmation and expansion phases) and overall, comparing with 6 months data in deferred treatment arm prior to treatment. Safety outcome captured in a separate long-term follow-up study (Protocol MGT010) for a further 4 years will be summarized separately.

1.3.2. Primary Efficacy Hypothesis

The objective of the dose expansion phase is to provide preliminary evidence of efficacy by comparing immediate treatment to a concurrent randomized control group. The randomized concurrent control eye refers to an untreated eye in a participant who was randomized to deferred treatment; these eyes are randomized and will receive treatment after completion of the 6-month deferral period. For the purposes of the primary efficacy analyses, these eyes represent the randomized concurrent control group. The primary comparisons of efficacy outcome assessments will be at Week 26 (immediate treatment vs. deferred treatment) in randomized expansion phase. Here immediate treatment group include subjects randomized to immediate low dose and immediate intermediate dose. Sensitivity analysis will also be conducted by pooling adult subjects from dose escalation and expansion phases together comparing immediate with deferred subjects.

The primary efficacy endpoint is responder/non-responder evaluated based on point-by-point data in full field from the 185-point (excluding 3 loci near blind spot) static perimetry assessed through Week 26 in the randomized immediate treatment subjects compared with randomized deferred subjects in the 26-week deferred period (prior to treatment). Subjects will be considered a responder if they experience at least 7 dB improvement from baseline at 5 or more loci at Week

26 and Week 13; this determination will be based on the treated eye for subjects in the immediate treatment group and for the deferred participant treatment eye in the deferred group, who had static perimetry assessments at both Week 13 and Week 26. The null hypothesis is that there is no difference in proportion of responders between randomized immediate treatment subjects and deferred treatment subjects. The alternative hypothesis is that the proportion of responders in the randomized immediate treatment subjects is greater than that in deferred subjects. The proportion of responders at Week 52 in subjects randomized for immediate treatment will also be estimated.

Table 1: loci near blind spot to be excluded from 185 loci grid for pointwise responder definition

| Eye | XPOS | YPOS |
|-------|-------|------|
| Left | -16 | -5.2 |
| Left | -13.9 | -1.2 |
| Left | -15 | 0 |
| Right | 16 | -5.2 |
| Right | 13.9 | -1.2 |
| Right | 15 | 0 |

1.3.3. Secondary Efficacy Hypothesis

For the expansion phase, the null hypothesis for each secondary endpoint listed below is that there is no difference between the treated eye in subjects for the immediate treatment at Week 26 and the deferred participant treatment eye in the deferred group during 26-Week deferred period prior to treatment. The alternative hypothesis for each secondary endpoint listed below is that the improvement in the ATIMP treated eye in immediate treatment subjects is greater than that on the deferred participant treatment eye during deferred period prior to treatment.

- a) Central 30-degree hill of vision (V30) in static perimetry using visual field modeling and analysis (VFMA) (Richard Weleber, 2015)
- b) Average threshold in mesopic microperimetry
- c) Maze walk time in Vision Mobility Assessment (VMA) under lux 1 and lux 4, separately
- d) Low Luminance visual acuity (LLVA)
- e) Patient report outcome, Low luminance questionnaire (LLQ) for the assessment of functional vision in low light conditions
- f) Contrast sensitivity (Log CS) as measured by Pelli-Robson
- g) Area of Intact EZ under the fovea from Optical Coherence Tomography (OCT)

1.4. Randomization and Blinding

In dose escalation phase, up to 18 adult participants will be administered one of 3 different doses of the ATIMP in cohorts of 3 participants at a time. Based on toxicity data, the IDMC will make a recommendation on the dose to administer to the next cohort of 3 participants.

Once an acceptable safety profile has been established in adults, the IDMC will agree the maximum tolerated dose in adults, which will be confirmed in 3 pediatric participants.

In the expansion phase, up to 48 subjects were randomized to 1 of 3 arms in a 1:1:1 ratio (Immediate low dose administration: Immediate intermediate dose administration: deferred administration). Subjects randomized to the deferred administration group were further randomized to receive the low or intermediate dose in a 1:1 ratio. The eye selected for administration was also randomized at the start of the expansion cohort. All aspects of randomization occurred on completion of screening. The three treatment groups of the randomized expansion phase will be stratified by age at date of informed consent (<25 years, \geq 25 years) to balance for disease severity between treatment groups with age used as a surrogate for severity.

Visual function assessors and reading centers are masked to treatment (dose levels and immediate vs. deferred treatment). Neither study site nor sponsor personnel were masked to treatment.

2. GENERAL ANALYSIS DEFINITIONS

2.1. Visit Windows

The following rules are applied to assign actual visits to analysis visit windows. If a subject has two or more actual visits in 1 visit window, the visit closest to the target day will be used as the protocol visit for that visit window. The additional visit(s) will not be used in the summaries or analyses, but they can be used for determination of clinically important outcomes. If two actual visits are equidistant from the target day within a visit window, the later visit is used. All assignments will be made in chronological order. Once a visit date is assigned to a visit window, it will no longer be used for a later time point. If a visit falls outside of the visit window, then this visit will be assigned to the closest window according to the distance to the target day and visit description, if there is no visit assigned to the visit window.

Table 1: Visit Windows

| Dose Escalation Phase, Pediatric Dose Confirmation Phase, and Immediate Treatment Arms of Expansion Phase | | |
|--|----------------------|-------------------|
| Visit Window Label | Time Interval | Target Day |
| Baseline | -6 Months - Day -1 | < Day 1 |
| Day 1 (ATIMP admin.) | Day 1 | Day 1 |
| Day 2 | Day 2 | Day 2 |
| Day 4 | Day 3 – Day 5 | Day 4 |
| Week 1 | Day 6 – Day 10 | Day 8 |
| Week 2 | Day 11 – Day 21 | Day 15 |
| Week 4 | Day 22 – Day 36 | Day 29 |
| Week 6 | Day 37 – Day 56 | Day 43 |

| Week 9 | Day 57 – Day 72 | Day 64 | |
|---|----------------------|---------------------|------------|
| Week 13 | Day 73 – Day 160 | Day 92 | |
| Week 26 | Day 161 – Day 259 | Day 183 | |
| Week 39 | Day 260 – Day 350 | Day 274 | |
| Week 52 | Day 351 – Day 393 | Day 365 | |
| Deferred Treatment Arms of Expansion Phase | | | |
| Period | Visit Window Label | Time Interval | Target Day |
| Deferred Period (prior to treatment) | Baseline | -6 Months - Day 1 | ≤ Day 1 |
| | Week 13 | Day 73 – Day 168 | Day 92 |
| | Week 26 | Day 169 – Day 365 † | Day 183 |
| Post treatment period | Day 1 (ATIMP admin.) | Day 1 | Day 1¶ |
| | Day 2 | Day 2 | Day 2¶ |
| | Day 4 | Day 3 – Day 5 | Day 4¶ |
| | Week 1 | Day 6 – Day 10 | Day 8¶ |
| | Week 2 | Day 11 – Day 21 | Day 15¶ |
| | Week 4 | Day 22 – Day 36 | Day 29¶ |
| | Week 6 | Day 37 – Day 56 | Day 43¶ |
| | Week 9 | Day 57 – Day 72 | Day 64¶ |
| | Week 13 | Day 73 – Day 160 | Day 92¶ |
| | Week 26 | Day 161 – Day 365 † | Day 183¶ |

¶: after ATIMP administration day for deferred subjects
 † : Any scheduled visits after week 26 in deferred treatment arm will be summarized as week 26 visits given COVID-19 delays

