to 4 days for baseline examinations, and 3 months, 6 months, 9 months and 12 months following ATIMP administration. For the deferred treatment arm, assessments will be performed at day 1, day 3, day 7, week 2, week 4, week 6, week 9, month 3 and month 6 after surgery. For day 1 and 3, refraction cannot reliably be measured. Therefore, the most recent refraction measurement will be used.

All participants (adults and children) will need to be able to perform reliable visual acuity testing, SD-OCT, retinal sensitivity testing (static visual fields, and visual mobility assessment, which are the principal clinical assessments both for safety and efficacy. Other clinical assessments will be undertaken as appropriate for the ability of individual participants, since there is wide variation in the abilities of individual children to perform such tests reliably; the evaluations for individuals may be restricted to those tests that they are able to perform reliably.

Additional assessments may be performed if considered appropriate for the management of any unexpected adverse effects. These may be submitted as urgent safety measures and protocol amendments performed where required. Conversely, tests that cannot be reliably performed by a participant may be discontinued for that participant. This is not anticipated for the aforementioned key clinical assessments because participants who are unable to perform such tests will be excluded from the study at the screening phase. Evaluation of safety and efficacy will also be performed on an individual participant basis. We do not anticipate that any discontinuation will affect significantly the overall quality of the safety and efficacy evaluation.

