Scheduled visits that cannot be conducted in person at the study site will be performed remotely/virtually, and site -based evaluations may be delayed until such time that on-site visits can be resumed. At each contact, participants will be interviewed to collect safety data. Key efficacy and safety endpoint assessments should be performed as feasible. Participants will also be questioned regarding general health status to fulfill any physical examination requirement.

The sponsor will continue to monitor the conduct and progress of the clinical study and any changes (eg, delay or discontinuation in recruitment, site monitoring and audits) will be communicated to the sites and health authorities according to local guidance. If a participant has tested positive for COVID 19, the investigator should contact the sponsor's responsible medical officer to discuss plans for study intervention and follow-up. Modifications made to the study conduct as a result of the COVID-19 pandemic should be summarized in the clinical study report.

GUIDANCE SPECIFIC TO THIS PROTOCOL

Each patient will be risk assessed on a case by case basis by the PI and his/her research team to decide the appropriate care for the patient.

Item	Item	Management of Item
no		
1	Missed assessments	Missed assessments will be captured in the EDC system as a
		deviation with the prefix COVID 19 RELATED.
2	Protocol Deviations	Any deviations to the study protocol due to COVID 19
		pandemic will be captured in the EDC system will be entered
		with the prefix COVID 19 RELATED.
3	Patient missing any scheduled visits	If scheduled visits cannot be conducted within the visit
		window the site can schedule an additional visit at the earliest
		opportunity the patient is able to travel,
4	Baseline Assessments	Baseline assessments for those patients who have had
		surgery postponed due to COVID 19 - these baseline
		assessments will be valid up to 6 months expect for
		Haematology, Biochemistry and Glucose which will need
		repeating.
5	Patients may be unable to attend study	It is acknowledged that this is a global crisis and patients may
	visit during visit window.	be put at more risk attending hospital appointments due to
		route of travel into research facility. If appropriate the
		sponsor will offer expenses for taxi fares to avoid busy train
		or bus routes.
		If patients are unable to reach their research facility but are
		able to seek help at a local ophthalmologist for urgent

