5.3. Primary Efficacy Endpoint

5.3.1. Definition

The primary efficacy endpoint is evaluated in subjects from the dose expansion phase based on point-by-point data from 185-point static perimetry assessed through Week 26 in the randomized immediate treatment subjects and compared with randomized deferred subjects in the 26-week deferred period (prior to treatment). Subjects will be considered a responder if they experience at least 7 dB improvement from baseline at 5 or more loci at Week 13 and Week 26; this determination will be based on the treated eye for subjects in the immediate treatment group and for the deferred participant treatment eye for subjects in the deferred group, who had static perimetry assessments at both Week 13 and Week 26. Subjects with missing visits in either Week 13 or Week 26 will not be counted as responder or non-responder and will not contribute to number of subjects in the denominator when calculating proportion of responders.

Treated eye refers to a treated eye in a participant who was assigned or randomized to immediate treatment in any period of the study. Randomized concurrent control eye refers to an untreated eye in a participant who was randomized to deferred treatment; these eyes will receive treatment after completion of the 6-month deferral period. For the purposes of the primary efficacy analyses, these eyes represent the randomized concurrent control group.

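### SAP 2.1 keeps one whole visit per window without requiring that it contains perimetry, so an on-time remote visit can displace valid later perimetry and remove the participant from the primary analysis

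*SAP*

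**What the plan says.** SAP 2.1 works on visits, not on assessments: "the visit closest to the target day will be used as the protocol visit for that visit window. The additional visit(s) will not be used". The exclusion covers summaries and analyses; the one exception lets extra visits inform clinically important outcomes. The SAP does not define that term or link it to any efficacy endpoint. Ties are settled by date: "If two actual visits are equidistant from the target day within a visit window, the later visit is used". The only fallback is for a window with no visit assigned, which may be filled by a visit from outside it.

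The windows in that section are:
- Week 13: Day 73 to 160 (immediate arms) and Day 73 to 168 (deferred period), target Day 92.
- Week 26: Day 161 to 259 (immediate arms) and Day 169 to 365 (deferred period), target Day 183.

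The primary endpoint (SAP 5.3.1) needs static perimetry at both time points. "Subjects with missing visits in either Week 13 or Week 26 will not be counted as responder or non-responder", and such participants also leave the denominator.

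Protocol Appendix 1 provides that scheduled visits which cannot take place on site are held remotely, and that site-based evaluations may wait until on-site visits resume. Item 3 covers visits that cannot be held in their window: in that case outside the "window the site can schedule an additional visit at the earliest" opportunity. Item 6 allows phone interviews for follow-up visits up to at least 3 months after surgery. SAP 1.2 records that the pandemic delayed or cancelled visits for several participants in the randomised phase.

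**The concern.** The rule asks which visit is nearest the target day. The analysis needs to know which perimetry result is nearest. The two questions have the same answer only when every visit in the window includes perimetry. A phone interview cannot include it, and an unscheduled safety check need not.

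The primary comparison is where this matters most, because both time points must be present and no imputation is planned for the responder endpoint. One displaced test at either time point discards the participant's whole contribution, although valid perimetry exists inside the SAP's own windows. V30, microperimetry, contrast sensitivity and maze time pass through the same rule. There the loss is one record in a mixed model, not the participant.

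The wording also leaves a choice open. SAP 1.4 states that sponsor personnel were not masked, and SAP 3 reports that efficacy was summarised at a data cut-off of 02 November 2020. What counts as a visit, and whether the exception rescues a perimetry result, should not be settled case by case.

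**Working it through.** The plan states no figure to reproduce: Protocol 5.7 gives no formal sample size calculation, and nothing states how often two visits fall in one window. The check is therefore whether the rule, applied as written, can discard usable perimetry.

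**Step 1: can scheduled visits alone cause it?** Put the protocol's tolerances around the SAP target days.
- Week 9: Day 64 ± 7 = Day 57 to 71; SAP window Day 57 to 72.
- Month 3: Day 92 ± 14 = Day 78 to 106; SAP window starts at Day 73 in both arms.
- Month 6: Day 183 ± 14 = Day 169 to 197; SAP window Day 161 to 259 (immediate), Day 169 to 365 (deferred).
- Month 9: Day 274 ± 14 = Day 260 to 288; SAP window starts at Day 260.

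Each of the Week 13 and Week 26 windows holds one scheduled visit. On schedule, nothing is displaced. A second visit must come from the remote, catch-up or unscheduled provisions.

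**Step 2: the displacement condition.** Let T be the target day, p the day of the visit with perimetry, and v the day of another visit in the window without it. The rule drops the perimetry if |v − T| < |p − T|, or if the distances are equal and v is later than p.

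**Step 3: illustrative days put in.**

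| Window (T) | Visit without perimetry | Visit with perimetry | Distances | Kept |
|---|---|---|---|---|
| Week 13, either arm (92) | phone, Day 92 | Day 120 | 0 vs 28 | Day 92 |
| Week 26, either arm (183) | remote, Day 183 | Day 210 | 0 vs 27 | Day 183 |
| Week 13, either arm (92) | unscheduled eye check, Day 95 | Day 104 | 3 vs 12 | Day 95 |

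Perimetry is dropped in all three rows. Day 120 lies outside the protocol's Day 78 to 106 and inside the SAP's Day 73 to 160. It is the kind of late visit that Appendix 1 item 3 permits and the wide window accepts. The third row rests on Protocol 5.4.2.3, which allows additional assessments for unexpected adverse effects. The SAP's fallback does not help, because a window holding a phone visit is not empty.

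**Step 4: consequence.** A participant is evaluable only if perimetry survives at Week 13 and at Week 26, so one displacement is enough. With maximum arm sizes of 32 (16 + 16) and 16, one loss is 1/32 = 3.1% of the immediate group or 1/16 = 6.25% of the deferred group.

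**Step 5: scale, for illustration only.** Responder rates and loss counts here are assumptions. Power is for an unstratified two-sided Fisher test at 0.05.

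| Evaluable (immediate vs deferred) | 40% vs 5% | 50% vs 10% |
|---|---|---|
| 32 vs 16 | 0.77 | 0.77 |
| 29 vs 14 | 0.67 | 0.73 |
| 24 vs 12 | 0.57 | 0.65 |

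This shows what a smaller denominator costs. It does not forecast how many would be lost.

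**The case against.** The strongest reply is that no sensible programmer would apply the rule this way. SAP 5.3.1 speaks of participants who had perimetry at both time points, and someone tested on Day 120 did have it. Delayed site testing may be entered under the same nominal visit as the phone contact and treated as one visit. The SAP does not say that a phone contact is an actual visit. Programming detail sits in the Data Presentation Specifications, which are not available here, and the SAP rests on protocol v12.0 while the supplied amendment log ends at v11.0. Appendix 1 item 3 is also a catch-up for a missed visit, not a second visit competing with a completed test battery.

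Much of this is fair, and the intended practice may well be sound. But the competitor in the example is a remote contact, not a completed battery, and Appendix 1 treats that contact as the way the scheduled visit is performed. SAP 2.1 bars additional visits from analyses in plain words, and SAP 5.3.1 does not say that it overrides them.

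A reader might go further and infer that ordinary multi-day testing triggers the loss, since the protocol allows up "to 4 days for baseline examinations, and 3 months, 6 months, 9 months and 12 months following ATIMP administration". The documents do not support that. It requires each calendar day to be its own visit. Protocol Tables 3 and 4 give Month 3 and Month 6 one visit number each, and SAP 2.5 refers to the end date of a visit, so a visit can span days. The 4-day allowance is stated only for baseline and for months after administration, not for the deferred arm's untreated Month 3 and Month 6. What remains is a gap: the SAP uses a single visit date ("Once a visit date is assigned to a visit window, it will no longer be used for a later time point") and does not say which date a multi-day visit takes.

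A reader might also infer that the immediate arms lose more because they have more follow-up visits. Those extra visits run from Day 2 to Week 9 and have their own windows, ending at Day 72. They cannot compete in Week 13 or Week 26.

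**Conclusion.** The point holds in a limited form. As written, SAP 2.1 can discard valid in-window perimetry when a remote or unscheduled visit without perimetry lies nearer the target, and SAP 5.3.1 then removes the participant from the primary comparison. Appendix 1 expressly foresees the sequence, and SAP 1.2 makes it plausible in this trial.

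The conclusion rests on two assumptions: that a remote or unscheduled contact counts as an actual visit, and that later site testing is dated as a separate visit. The documents settle neither. The frequency is unknown, so no expected loss can be stated, and neither can the arm more affected. The deferred arm's wider Week 26 window does not itself create extra visits.

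This is a free improvement: a stated rule can be replaced by a better one at no cost. It is not evidence that the primary analysis has lost participants.

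**What to change.** Replace the selection sentences in SAP 2.1 with wording such as:

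> Window selection is made separately for each assessment. Among the non-missing results of that assessment in the window, the one closest to the target day is used; if two are equidistant, the later is used. All dates belonging to one nominal visit count as one visit.

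In each row of the Step 3 table this selects the perimetry result, because it is the only non-missing one in its window. It also closes the multi-day gap.

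Two checks should go with it. First, list participants with perimetry inside a Week 13 or Week 26 window but not on the selected visit. This gives the count the documents lack, and the COVID-19 visit tabulation in SAP 4.4 is a natural place for it. Second, confirm that Appendix 1 and the visit-duration text read the same in protocol v12.0.

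The cost is a short SAP edit and a programming check, with no new data and no change to endpoint, test or alpha.
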